#### 5.3.2.2. Derivation Rules

Total mRSS score will be analyzed as reported by the investigator, considering that all individual scores are completed, no imputation will be done on the primary efficacy endpoint.

#### 5.3.2.3. Analysis Methods

The following analyses will be done on the FAS as the primary analysis, and repeated on the PP Analysis Set, if more than 10% of the subjects have at least one major protocol deviation, to confirm the results of the primary analysis:

The mRSS and change from baseline in mRSS score (primary endpoint) will be summarized by descriptive statistics. Mean ( $\pm$ SE) plots over time (analysis visits based on time window) for both treatment groups, and similar mean ( $\pm$ SE) plots for the change from baseline will be presented. Additionally, spaghetti plot of change from baseline will be displayed with subjects presented by treatment.

Change from baseline in mRSS will be analyzed using a mixed-effects model for repeated measures (MMRM). The model will include treatment and visit as fixed effects, baseline mRSS and country as covariates, and treatment-visit as interaction terms. Subject will be included in the model as a random effect. The likelihood-based MMRM will be performed using a SAS PROC MIXED procedure (see [Appendix 3](#)), and the Kenward-Roger method for degrees of freedom will be applied. The restricted maximum likelihood (REML) method will be used for estimation. The Least Square (LS) means along with the associated SE and 95% CIs, as well as the difference in LS means and associated 95% CIs will be displayed at each time point. For exploratory purpose only, p-values will also be displayed for testing the difference in LS means at each timepoint. The p-value derived for the overall difference between treatment groups will also be displayed, as well as all p-values for fixed effects included in the model.

The variance-covariance matrix will be assumed to be unstructured. If the procedure does not converge then a compound symmetric variance-covariance matrix will be used instead.

The number and percentage of subjects with a clinically meaningful change in skin score (as defined in section 5.3.2.2) will be summarized by treatment. Incidence will be derived overall (at any post-baseline timepoint) and for each analysis visit.

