#### 7.3.5.1. Analysis for Primary Efficacy Endpoint

Change from baseline in mRSS will be presented descriptively and graphically over time by treatment group.

Change from baseline in mRSS will be analyzed using a mixed-effects model for repeated measures (MMRM). The model will include treatment and visit as fixed effects, baseline mRSS and country as covariates, and treatment-visit as interaction terms. Least square (LS) means with 95% confidence intervals (CIs) will be calculated from the model at each time point as well as difference from placebo in LS means with 95% CIs.

The number and percentage of subjects with a clinically meaningful change in skin score (as defined in Section 6.5.1) will be summarized by treatment.

Change from baseline in mRSS will also be analyzed for a series of subgroups (such as baseline characteristics and background treatment). Details will be provided in the SAP.

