## 2.2. STUDY ENDPOINTS

### Primary Endpoint

- Change from baseline in mRSS over 24 weeks, i.e. over the entire treatment period as well as at each timepoint.

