### 5.3.1. Level of Significance

All statistical tests will be 2-sided and performed at the 5% significance level, thereby providing 95% (2-sided) CIs. However, given the exploratory nature of this proof-of-concept study, the success of the study will be based on the evaluation of all analysis results, including safety profile and descriptive analysis of all efficacy endpoints.

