i If Visit 9 (Week 24) cannot be conducted within the time window of ±4 days, the visit window can be extended to ±28 days (i.e. can be extended or shortened up to 28 days) to enable conduct of the visit on site. If Visit 9 is conducted after Week 24, additional regular phone calls at Week 24 and every 14 days thereafter should be implemented, until an on-site Visit 9 can take place, or until Week 32, to evaluate the subject’s safety. In addition, if any of the follow-up visits cannot be performed on-site, a phone call to evaluate the subject’s safety should be performed on the date of the visit. The information to be collected during these phone calls is detailed in Protocol Section 6.6.

j The FU visits need to be scheduled in relation to the last dose of IMP. FU1 should be 28 days ±7 days after the last IMP administration, and FU2 should be 84 days ±7 days after the last IMP administration.

[REDACTED]

[REDACTED]

- | [REDACTED]
- | [REDACTED]
- | [REDACTED]
- | [REDACTED]

[REDACTED]

[REDACTED]

[REDACTED]

[REDACTED]

[REDACTED]

[figure not shown]
[REDACTED]

[REDACTED]

[REDACTED]

### APPENDIX 3

The below SAS code represents the analysis model used for the primary efficacy variable analysis.

The variance-covariance matrix will be assumed to be unstructured. If the procedure does not converge then a compound symmetric variance-covariance matrix will be used instead

Signature Page for glpg1690-cl-204-sap 15149

Approval	 Biostatistician Biometrics 06-Aug-2020 07:26:08 GMT+0000
----------	--

Approval	 07-Aug-2020 11:19:13 GMT+0000
----------	---

Signature Page for glpg1690-cl-204-sap 15149

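### The primary mRSS model pairs an unstructured covariance with a redundant random subject effect, and its only fallback, plain compound symmetry, gives wrong per-visit confidence intervals when the SD of change differs by visit

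*SAP*

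**What the plan says.** Protocol 7.3.5.1 gives the model for the primary endpoint: "The model will include treatment and visit as fixed effects, baseline mRSS and country as covariates, and treatment-visit as interaction terms". It names no random subject effect, no covariance structure and no fallback.

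SAP 5.3.2.3 keeps these terms and adds: "Subject will be included in the model as a random effect". It then states: "The variance-covariance matrix will be assumed to be unstructured". The single contingency is: "If the procedure does not converge then a compound symmetric variance-covariance matrix will be used instead". Estimation is by REML in PROC MIXED with Kenward-Roger degrees of freedom; no robust standard error is mentioned. Appendix 3 repeats the covariance rule and introduces the code with "The below SAS code represents the analysis model used for the primary efficacy variable analysis", but the code itself is not visible in the text available.

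SAP 2.2 defines the primary endpoint "over the entire treatment period as well as at each timepoint". SAP 5.3.2.3 displays LS mean differences with 95% CIs at each visit, and adds: "For exploratory purpose only, p-values will also be displayed for testing the difference in LS means at each timepoint". SAP 5.1, which lists changes to the planned analyses, does not mention the random subject effect.

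**The concern.** There are two linked problems.

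First, an unstructured matrix already covers every variance and covariance within a subject. A random subject intercept on top of it cannot be separated from that matrix. The total covariance, LS means and SEs remain identified, but the information matrix for the covariance parameters is singular. That creates an avoidable risk of a singular Hessian or of non-convergence, and non-convergence is what triggers the fallback.

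Second, the fallback goes directly to the structure that gives all visits the same variance. If the SD of change grows over time, the Week 24 interval is too narrow and the Week 4 interval too wide; if it shrinks, the reverse. Kenward-Roger adjusts for uncertainty in the covariance estimates, not for a wrong structure. The per-protocol repeat and the sensitivity analyses in SAP 5.3.3 use the same model, so they would not reveal the error.

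What is at stake is the reported precision at individual visits, including Week 24, for an endpoint that the SAP defines at each time point.

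**Working it through.** **Inputs.** From Protocol 7.1 and SAP 2.6: 20 and 10 subjects, 10% dropout (hence 18 and 9), one common SD of 5, a true difference of 4.7. From Protocol 6.5.1: on-treatment post-baseline mRSS at Weeks 4, 8, 16 and 24. From SAP 5.3.1: two-sided 5% level. The documents give no SDs by visit and no correlations, so those below are assumptions shown as a range.

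**The plan's own figure.** SE = 5 × √(1/18 + 1/9) = 2.041. P(observed difference > 4) = Φ((4.7 − 4)/2.041) = Φ(0.343) = 63.4%. The stated 63% reproduces, so 18 vs 9 and SD 5 are the right base.

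**Redundancy.** Four visits give 4 × 5/2 = 10 unstructured parameters. Adding a random intercept gives V = σ²_b·J + R, where J is the matrix of ones. Any change in σ²_b can be offset by subtracting a constant from every element of R. The rank of the derivatives of V confirms this:
- unstructured: 10 of 10
- unstructured + random intercept: 10 of 11
- compound symmetry + random intercept: 2 of 3, so the redundancy persists in the fallback
- heterogeneous compound symmetry: 5 of 5

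The smallest eigenvalue of the information matrix is 0.0067 for unstructured alone and zero to rounding with the random intercept added.

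**Effect of the fallback.** With complete data, compound symmetry estimates one variance, the mean of the visit variances. The Week 24 SE is therefore off by the factor (root-mean-square SD)/(Week 24 SD). For SDs 3.5, 4, 4.5, 5: √((12.25 + 16 + 20.25 + 25)/4) = √18.375 = 4.287, and 4.287/5 = 0.857. Type I error at Week 24 comes from 40,000 null trials per scenario, 18 vs 9, complete data, correlation 0.7 (exchangeable or decaying with time), with the fallback applied to every trial.

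| SDs at Weeks 4/8/16/24 | RMS SD | Week 24 SE ratio | Week 24 type I error |
|---|---|---|---|
| 5/5/5/5 | 5.000 | 1.000 | 4.9–5.1% |
| 4.5/4.7/4.85/5 | 4.766 | 0.953 | 6.1% |
| 3.5/4/4.5/5 | 4.287 | 0.857 | 8.9–9.2% |
| 2.5/3.5/4.5/5 | 3.992 | 0.798 | 11.8% |
| 6.5/6/5.5/5 | 5.777 | 1.155 | 2.4–2.5% |

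The unstructured fit held 4.8–5.1% at Week 24. At Week 4 the error under compound symmetry runs the other way: with SDs 3.5–5 the SE is 4.287/3.5 = 1.22 times too large and rejection falls to 1.7–1.8%; with SDs 2.5–5 it falls to 0.3%. The overall, visit-averaged treatment test stayed at 4.9–5.1% in every scenario.

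**Interval width.** The mean Week 24 half-width is 4.2 points unstructured, against 3.5 (SDs 3.5–5) or 3.3 (SDs 2.5–5) under compound symmetry. An observed difference of 4, the plan's own benchmark, would typically read 4 ± 4.2 = −0.2 to 8.2 unstructured, but 4 ± 3.5 = 0.5 to 7.5 under compound symmetry.

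**Cross-checks.** A separate run with other SD paths gave Week 24 coverage of 92–93% (SDs 4 to 5), 90% (3 to 5), 87% (2.5/3.3/4.2/5) and 85–86% (SD growing with the square root of time). With 20 vs 10, a baseline covariate and three random dropouts (1,500 trials, approximate degrees of freedom), Week 24 rejection was 9.5–9.9% (SDs 3.5–5) and 10.8–12.1% (SDs 2.5–5), and the overall test was 4.4–5.5%.

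**The proposed alternative.** Heterogeneous compound symmetry by REML, with Satterthwaite degrees of freedom standing in for Kenward-Roger (3,000 trials per scenario), gave Week 24 rejection of 4.4–5.3% with exchangeable correlation and 3.6–3.8% with decaying correlation. All fits converged.

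**The case against.** The strongest objection is that nothing shows the fallback would be reached. Harm requires that the code contains both a random and a repeated specification, that the fit fails to converge, and that SDs differ by visit. In a purpose-written REML routine (20 vs 10, three dropouts, no country term), unstructured plus random intercept converged in 240 of 240 simulated trials, as did unstructured alone, and Week 24 SEs agreed to within 0.005%. The trigger is non-convergence, not a singular Hessian: a fit that converges with a redundant term stays unstructured and reports the same LS means and SEs. This stands as a limit on how often the fallback might be used. It is not evidence about PROC MIXED, and it does not touch what the fallback does once used.

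The Appendix 3 code cannot be seen. If it uses only a REPEATED statement, the random-effect point becomes a wording conflict to align. That also stands. The protocol calls the model mixed-effects and leaves details to the SAP, so the absence of this term from SAP 5.1 is a minor matter.

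Per-visit p-values are labelled exploratory, SAP 5.3.1 rests success on all results together, and descriptive SDs by visit would be shown beside the model output. This limits the consequence but does not correct an interval with the wrong width.

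Finally, the choice among structures with visit-specific variances is partly preference, and heterogeneous compound symmetry is itself mildly misspecified when correlation decays. That is fair; the cost is slight conservatism.

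**Conclusion.** The concern holds. On the SAP's wording the random subject effect is redundant both with the unstructured matrix and with the fallback. Plain compound symmetry gives wrong visit-specific CIs whenever SDs differ by visit. With SD 5 at Week 24 and 18 vs 9 completers, the Week 24 SE is 5% to 20% too small for the rising-SD paths examined (type I error 6.1% to 11.8%) and 16% too large for the falling path (2.4–2.5%). It is correct if SDs are equal.

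These figures are conditional on the fallback being used and on assumed SD paths; they are not operating characteristics of the whole plan. The non-convergence rate in PROC MIXED is unknown. With complete data the overall treatment test is unaffected, and no decision rule depends on Week 24 significance. The damage is confined to the reported per-visit precision. It is worth correcting because the correction is cheap, but it does not undermine the trial.

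**What to change.** In SAP 5.3.2.3, delete the random-effect sentence, or state that within-subject correlation is modelled only through a REPEATED statement with subject identifier and TYPE=UN. Make Appendix 3 match.

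Replace the fallback sentence with an ordered rule: if the unstructured fit does not converge, use heterogeneous compound symmetry (a separate variance per visit, one common correlation) with Kenward-Roger; use plain compound symmetry only if that also fails. Heterogeneous Toeplitz or AR(1) would also keep visit-specific variances but are not needed: they tie correlation to visit order, whereas the visits are 4, 8 and 8 weeks apart.

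The cost is two sentences and alignment of the appendix. If the fallback is used, it estimates 5 covariance parameters instead of 2. Its Week 24 half-width is 4.1–4.4 points, against 4.2 unstructured, and it is slightly conservative (3.6–3.8%) if correlation decays with time. Without the random effect, 212 of 212 unstructured fits with 30 subjects and three dropouts converged in a purpose-written routine. This is only indicative for PROC MIXED, but it suggests that the fallback should rarely be needed.

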**5.3.3. Sensitivity of Primary Endpoint**

**5.3.3.1. Derived mRSS**

**5.3.3.1.1. Definition**

If more than 10% of subjects have missing mRSS total score at Week 24, then the change from baseline in derived mRSS will be analyzed over 24 weeks to confirm the results of the primary efficacy analysis.

There will be an additional sensitivity analysis for subjects that did not have a Week 24 at all within the extended window, but possibly in the Week 28 - Week 32 interval. These subjects will be off IMP in that period. The primary endpoint analysis will be repeated including the closest mRSS assessment to the original Week 24 target (Day 169) up to and including Week 32 (Day 225).

**5.3.3.1.2. Derivation Rules**

Total mRSS score will be derived from individual mRSS scores at each visit if at least 14 of the 17 items are not missing. At each visit, the derived score will be:

$$(\text{Sum of all non-missing items}) * 17 / (\text{number of non-missing items})$$

**5.3.3.1.3. Analysis Methods**

Derived mRSS will be analyzed, mean (±SE) plots over time and spaghetti plot will be produced, as specified in section 5.3.2.3.

**5.3.4. Other Efficacy Parameters**

[Redacted]

[Redacted]

[Redacted]

[Redacted]

[Redacted]

---

[REDACTED]

[REDACTED]

[REDACTED]

[REDACTED]

[REDACTED]

[REDACTED]

[REDACTED]

[REDACTED]

[REDACTED]

[REDACTED]

[REDACTED]

[REDACTED]

[REDACTED]

[REDACTED]

[REDACTED]

[REDACTED]

[REDACTED]

[REDACTED]

[REDACTED]

[REDACTED]

[REDACTED]

[REDACTED]

[REDACTED]

[REDACTED]

[REDACTED]

[REDACTED]

[REDACTED]

[REDACTED]

[REDACTED]

[REDACTED]

[REDACTED]

[REDACTED]

[REDACTED]

[REDACTED]

[REDACTED]

---

[REDACTED]

[REDACTED]

[REDACTED]

[REDACTED]

[REDACTED]

[REDACTED]

[REDACTED]

[REDACTED]

[REDACTED]

[REDACTED]

[REDACTED]

[REDACTED]

[REDACTED]

[REDACTED]

---

[REDACTED]

[REDACTED]

[REDACTED]

[REDACTED]

[REDACTED]

[REDACTED]

[REDACTED]

[REDACTED]

[REDACTED]

[REDACTED]

[REDACTED]

[REDACTED]

[REDACTED]

[REDACTED]

[REDACTED]

[REDACTED]

[REDACTED]

[REDACTED]

[REDACTED]

[REDACTED]

[REDACTED]

[REDACTED]

[REDACTED]

[REDACTED]

[REDACTED]

[REDACTED]

[REDACTED]

[REDACTED]

[REDACTED]

[REDACTED]

[REDACTED]

[REDACTED]

[REDACTED]

### 5.3.5. Subgroup Analyses

Actual values and change from baseline in mRSS [REDACTED] will be summarized over the 24-weeks for the following subgroups:

- [REDACTED]

- mRSS baseline score:  $< 20$  or  $\geq 20$  points

## 5.4. SAFETY ANALYSES

Safety analyses will be performed on the Safety Set.

No formal testing will be performed to compare the treatment groups.

Tabulations will be shown by treatment group.

---

### 5.4.1. Adverse Events

All adverse events (AEs) and changes in attributes (worsening and improvement) of AEs are reported in the database. An identification number serves to link the records considered by the investigator as describing the evolution of one and the same event.

#### 5.4.1.1. Definition of Treatment-Emergent Adverse Events

The analysis of adverse events will be based on treatment-emergent events (TEAE). TEAEs are defined as

- For subjects not entering the OLE study: AEs having a start date equal or after the date of the first IMP administration and up to the last dose date + 30 days.
- For subjects who entered the OLE study: AEs having a start date equal or after the date of the first IMP administration and up to the date of last double-blinded IMP dose date + 30 days or the date of first OLE IMP administration (excluded), whichever comes first.
- And is either a newly reported event, or a worsening\* of an existing event. Improvements are not considered treatment-emergent.

\*Worsening is defined as worsening in at least one of the following attributes: seriousness, severity, relationship and/or action taken.

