**Figure 1: Schematic Study Overview**

D=Day, FU=Follow-up, V=Visit, W=Week.

\* This will be a phone call to assess safety (no clinical study center visit).

For the in- and exclusion criteria please refer to Section 4.5.1, “[Inclusion Criteria](#)” and Section 4.5.2, “[Exclusion Criteria](#)”.

The subjects will visit the clinical study center at screening/Visit 1 (Day -28 to Day -1), Day 1/Visit 2 (baseline), Day 15 (Week 2/Visit 3), Day 29 (Week 4/Visit 4), Day 57 (Week 8/Visit 5), Day 113 (Week 16/Visit 7), Day 169 (Week 24/Visit 9), and, if applicable, the ED visit. At Weeks 12 (Visit 6) and 20 (Visit 8), a phone call will be made to assess safety. In addition, a follow-up visit will be planned 4 weeks after the last administration of IMP (Day 197 [Week 28]) (i.e. Follow-up Visit 1) and a second follow-up visit will be planned 12 weeks after the last administration of IMP (Day 253 [Week 36]) (i.e. Follow-up Visit 2). Additional unscheduled visits are allowed for any safety assessments if clinically indicated (see Section 6.2).

For any subjects who, due to any COVID-19-related reason, cannot perform Visit 9 (Week 24), within the time window of  $\pm 4$  days, the window for the visit may be increased to  $\pm 28$  days.

Each subject will be in the study for up to approximately 40 weeks (up to 4 weeks of screening, 24 weeks of treatment, and 12 weeks of follow-up). Covid-19 mitigation measures may increase the time in the study up to approximately 44 weeks.

For detailed info regarding dosage form, packaging, and labeling of the IMP, please refer to Section 5.2, “[Dosage and Administration](#)” and Section 5.3, “[Packaging, Labeling, and Distribution](#)”.

The end of the study (EoS) is reached when the last visit of the last subject is performed.

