#### 7.3.6.2. Adverse Events

Clinical and laboratory AEs will be coded using the latest version of the Medical Dictionary for Regulatory Activities. System Organ Class (SOC), High Level Group Term, High-Level Term, Preferred Term, and Lower-Level Term will be attached to the clinical database.

The following AEs will be considered as treatment-emergent AEs (TEAEs):

Any AE with an onset date on or after the start of IMP intake and no later than 30 days after last dose of IMP, or any worsening of any AE on or after the start of IMP intake.

AEs reported before the start of IMP or later than 30 days after the last dose of IMP will be listed.

In addition, summaries and/or listings will be provided for the suspected symptoms/AEs of flare with an onset date on or after the IMP start date until the EoS (including information from Follow-up Visit 2).

Summaries (number and percentage of subjects) of TEAEs per subject by SOC and Preferred Term will be provided by treatment group. TEAEs will also be summarized by causal relationship to IMP and severity. In addition, TEAEs leading to premature discontinuation of IMP will be summarized and listed. Also, all SAEs, including the non-treatment-emergent SAEs, will be listed.

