### Secondary Endpoint

- Incidence of treatment-emergent adverse events (TEAEs), serious adverse events (SAEs), adverse events (AEs), and tolerability of GLPG1690 over 24 weeks

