**Table 1: Analysis Periods**

Analysis Period	Start Analysis Period	End Analysis Period
Screening	Date of signing the ICF.	Date of first IMP intake - 1 day
Treatment	Date of first IMP administration.	For subjects not entering CL-206 study: date of last intake of IMP + 30 days.  For subjects who entered the CL-206 study: the date of last intake of IMP + 30 days or the date of first OLE IMP administration (excluded), whichever comes first.
Post-Treatment	End date of the treatment period + 1 day.	Date of last contact in CL-204 study. For subjects who entered the CL-206 study this will be the date of first OLE IMP administration.

ICF: informed consent form

The last analysis period will always end on the date of last contact, collected on the Study Completion/Discontinuation of Study eCRF page, whichever is earliest.

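### The secondary endpoint is adverse-event incidence over 24 weeks, but the TEAE window is not 24 weeks long and its length depends on whether the subject enters the open-label extension

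*SAP*

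**What the plan says.** **Endpoint.** Protocol 4.3.2 and SAP 2.2 both define the secondary endpoint as "Incidence of treatment-emergent adverse events (TEAEs), serious adverse events (SAEs), adverse events (AEs), and tolerability of GLPG1690 over 24 weeks".

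**SAP counting rule.** SAP 5.4.1.1 has two windows.
- Subjects who do not enter the OLE are counted "up to the last dose date + 30 days".
- Subjects who do enter are counted to last double-blind dose plus "30 days or the date of first OLE IMP administration (excluded), whichever comes first". SAP Table 1 ends the treatment period in the same way: "the date of last intake of IMP + 30 days or the date of first OLE IMP administration (excluded), whichever comes first".

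Worsening is a further condition inside these dates ("And is either a newly reported event", or a worsening of an existing one), so it is bounded too.

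**Protocol counting rule.** Protocol 7.3.6.2 counts new events with onset "no later than 30 days after last dose of IMP", "or any worsening of any AE on or after the start of IMP intake". The worsening clause has no end date, and nothing is said about stopping at the first OLE dose.

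**Tables.** SAP 3.5.3 sets the denominator for event data as all subjects in the analysis set and period. SAP 5.4.1.5 and 5.4.1.8 plan numbers and percentages of subjects with TEAEs. The readable text plans no 24-week cut in the TEAE definition and no exposure-adjusted or time-to-event summary.

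**Timing.** SAP section 4 bases the primary-analysis output on data up to the Week 24 visit, with a final analysis after the post-treatment period.

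**The concern.** Safety and tolerability against placebo over 24 weeks is the trial's only secondary objective. The planned percentages answer a different question: the share of subjects with an event in a window that closes at different times for different subjects. What closes it is OLE entry, which is decided after randomisation and may be related to tolerability. A reader of the clinical study report would see a crude percentage under a 24-week endpoint, although part of it was gathered over about four further weeks, and only in subjects who did not roll over.

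There is also a gap in the record of changes. Protocol section 7 requires departures from the protocol to be justified in the SAP. SAP 5.1 lists neither the stop at the first OLE dose nor the bounded worsening rule. It does adapt the per-protocol set and the mRSS sensitivity analysis to late Week 24 visits, but makes no matching change for adverse events.

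**Working it through.** The documents give no adverse-event rate and no rollover rate, so there is no plan figure to reproduce on this point. The window lengths follow from the documents; the incidences below are illustrations.

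**Step 1: days counted.** Inputs are Day 169 for Visit 9 (protocol 4.1), a COVID-19 window of 28 days either way for that visit (protocol 6.1), dosing to Week 28 at the latest (protocol 5.3), rollover to Week 32 at the latest (protocol 4.1), and the SAP 5.4.1.1 rules. I assume the first OLE dose is taken on the rollover day. Days run from Day 1, inclusive.

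| Subject | Counting ends | Days | Weeks |
|---|---|---|---|
| Rolls over on Day 169 | Day 168 | 168 | 24.0 |
| No rollover, last dose Day 168 | 168 + 30 | 198 | 28.3 |
| COVID-19: Visit 9 and rollover on Day 141 | Day 140 | 140 | 20.0 |
| COVID-19: Visit 9 and rollover on Day 197 | Day 196 | 196 | 28.0 |
| COVID-19: last dose Day 197, rollover on Day 225 | earlier of Day 227 and Day 224 | 224 | 32.0 |
| COVID-19: no rollover, last dose Day 196 | 196 + 30 | 226 | 32.3 |
| Example: stops treatment on Day 100 | 100 + 30 | 130 | 18.6 |

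A last dose one day later (Day 169 or Day 197) adds one day where the 30-day rule sets the end.

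**Step 2: effect on a crude percentage.** Assume a constant first-event hazard that continues unchanged after the last dose. If the 24-week incidence is p, the incidence over d days is 1 − (1 − p)^(d/168).

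| p at 168 days | 198 days | 226 days |
|---|---|---|
| 10% | 11.7% | 13.2% |
| 50% | 55.8% | 60.6% |
| 70% | 75.8% | 80.2% |

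For p = 50% and d = 198: 1 − 0.5^(198/168) = 1 − 0.5^1.179 = 55.8%. In the other direction, d = 140 gives 43.9%.

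**Step 3: effect on the comparison of arms.** Give both arms the same hazard and let a proportion r roll over on Day 169. The crude percentage is r × I(168) + (1 − r) × I(198), so two arms differ by the difference in r times I(198) − I(168). Take assumed rollover of 90% and 60%:
- p = 10%: 0.3 × (11.7 − 10.0) = 0.5 points.
- p = 50% or 70%: 0.3 × 5.8 = 1.7 points.

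Equal rollover gives zero. The extreme of 100% versus 0% gives 5.8 points at p = 50% or 70%. For scale, one subject is 1/20 = 5 points in the active arm and 1/10 = 10 points in the placebo arm.

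**The case against.** Last dose plus 30 days is a normal on-treatment window, and counting has to stop at the first OLE dose because placebo subjects then receive active drug. SAP 5.4 plans no formal safety testing, and SAP 5.3.1 calls the study exploratory. Planned output already shows exposure duration, OLE entry and each event's start day. At 20 versus 10 subjects, the arm distortion in Step 3 is a fraction of one subject. All of this stands, and it limits the point to a modest one. It does not turn the final tables into 24-week incidences.

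Three stronger readings are tempting, and the documents do not support them.

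- **That worsening is counted without limit.** Only the protocol's worsening clause lacks an end date. The SAP rule that builds the tables bounds it, and the protocol's next sentence sends events reported more than 30 days after the last dose to listings. This is a wording mismatch to reconcile.
- **That no planned table estimates 24-week incidence.** SAP section 4 may already cut the primary-analysis tables near Week 24. If the cut is applied per subject, they come close. If it is one calendar cut-off, subjects enrolled early contribute follow-up beyond Week 24. The section does not say which.
- **That the less tolerable arm is counted for longer.** Subjects who finish and decline the OLE are counted longer, but someone who stops on Day 100 is counted to about Day 130, less than a rollover completer. The direction is not fixed.

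**Conclusion.** The point holds as a mismatch between the stated endpoint and its estimator. It is established for the final analysis and left unclear for the primary analysis. The window differs by about 30 days between completers who roll over on time and those who do not, and ranges from about 20 to 32 weeks under the COVID-19 provisions; early discontinuers can have less. These lengths follow from the documents, given an OLE first dose on the rollover day.

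The sizes rest on assumptions: a constant hazard, illustrative event rates and invented rollover rates. On that basis, the percentage in subjects who do not roll over on the normal schedule is about 2 to 6 points above its 24-week value, and the arm comparison moves by 0.5 to 1.7 points at 90% versus 60% rollover. That is too small to change a decision in a descriptive study of this size. The change is worth making because the stated endpoint is otherwise not clearly reported, and making it costs little.

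**What to change.** 1. Keep the existing last dose plus 30 days TEAE tables. Events in subjects still taking study drug after Day 169 must remain visible.
2. In SAP 5.4.1.8, add a summary of TEAEs and serious TEAEs with onset or worsening up to a common Day 169 cut, or the first OLE dose if earlier, and label it as the 24-week endpoint.
3. In the same section, add exposure-adjusted incidence by arm: subjects with an event divided by total time at risk. The Day 169 cut alone does not equalise follow-up for early discontinuers or for Week 20 rollovers, so both additions are needed.
4. In SAP section 4, state how the Week 24 data cut applies to adverse-event tables: per subject or by one calendar date.
5. In SAP 5.1, list the stop at the first OLE dose and the bounded worsening rule as differences from protocol 7.3.6.2.

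No new data are needed. The cost is a little extra programming and a few lines of SAP text. The downside is that events after Day 169 appear only in the existing tables and not in the one labelled as the 24-week endpoint.
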